# 4.5.2 Measurements of Treatment Compliance

Compliance to the study treatment regimen will be summarized by treatment group, separately for each study treatment period as well as over the entire study participation. Compliance will be determined based on tablet count entries made on the Study Drug Dispensing and Accountability eCRF pages. Expected dosing will be based on the onsite dosing administration:

- The expected tablet dosing for Double-Blind Treatment Period is considered to be the on-site dose from Day 1 to the Treatment Completion or Treatment Discontinuation Date on the End of Treatment (Double-Blind eCRF), plus 1. The number of dosing days is then multiplied by two to account for two tablets of EP-547 or placebo taken each day.
- The expected tablet dosing for Open-Label Extension Period is considered to be the on-site dose from the Week 6 Study Drug Administration (On-site) eCRF to the Treatment Completion or Treatment Discontinuation Date on the End of Treatment (Open-Label eCRF), plus 1. The number of dosing days is then multiplied by two to account for two tablets of EP-547 taken each day.

The actual number of doses (tablets) received will be determined based on the number of tablets taken reported on the Study Drug Dispensing and Accountability eCRF. The number of tablets taken in the Double-Blind Treatment Period and Open-Label Extension Period will be assessed based on the defined treatment period windows (using the date ranges calculated in the expected dosing derivation) and the kit dispense dates.

Treatment compliance will then be calculated as the actual number of tablets taken divided by the expected number of tablets taken, multiplied by 100 for each treatment period and overall.

The number and percentage of subjects who are < 80% compliant and  $\ge 80\%$  compliant within each treatment group will be summarized separately for each study treatment period, as well as for overall study participation.

#### 4.5.3 Adverse Events

Treatment-emergent adverse events are defined as those AEs with onset after the first dose of study drug or existing events that worsened after the first dose during the study. Treatment-emergent AEs will be summarized by treatment group separately for each study treatment period and overall, within each study treatment period. An overall TEAE summary, incidence of TEAEs by system organ class and preferred term, and summary of the most frequently-occurring TEAEs will also be presented for both periods combined (i.e., overall study) for the Safety Analysis Set and the Open-Label Extension Analysis Set. Adverse events will be considered treatment-emergent relative to the study treatment period where the onset of the AE occurred; any TEAE that begins in the Double-Blind Treatment Period will be considered treatment-emergent in the Double-Blind Treatment Period only. The same logic is to be applied to the Open-Label Extension assessment; the Week 6 Study Drug Administration (On-site) entry will be considered the start of Open-Label Extension dosing for assessing treatmentemergence. Events reported with a partial onset date (e.g., month and year are reported but the day is missing) will be considered to be treatment-emergent in both treatment periods if it cannot be confirmed that the event onset was prior to the first dose of study drug for a specific treatment period based on the available date entries. Events with date and time present will be compared against the treatment start date and time to determine treatment-emergence.

Verbatim terms on case report forms will be mapped to preferred terms and system organ classes using MedDRA, version 25.0.

Summaries that are displayed by system organ class and preferred terms will be ordered by descending incidence of system organ class and preferred term within each system organ class. Summaries displayed by preferred term only will be ordered by descending incidence of preferred term. Inclusion criteria assessments for frequency-related summaries will be made separately for each study treatment period and study overall. Summaries of the following types will be presented:

- Overall summary of number of unique TEAEs and treatment-emergent SAEs and subject incidence of TEAEs meeting various criteria;
- Subject incidence of TEAEs by MedDRA system organ class and preferred term;
- Subject incidence of the most frequently-occurring TEAEs (i.e., TEAEs occurring in ≥ 10% of the Safety Analysis Set or Open-Label Extension Analysis Set) by MedDRA preferred term;
- Subject incidence of TEAEs by CTCAE severity grade, MedDRA system organ class, and preferred term;

- Subject incidence of TEAEs by relationship to study drug, MedDRA system organ class, and preferred term;
- Subject incidence of TEAEs of Special Interest by MedDRA system organ class and preferred term;
- Subject incidence of the most frequently-occurring TEAEs related to study drug (i.e., related TEAEs occurring in ≥ 10% of the Safety Analysis Set or Open-Label Extension Analysis Set) by MedDRA preferred term;
- Subject incidence of CTCAE grade 3 or higher TEAEs related to study drug by MedDRA system organ class and preferred term; and
- Subject incidence of SAEs by MedDRA system organ class and preferred term.

A summary by safety subgroups of interest (type of cholestatic disease and baseline eGFR) described in Section 4.4.7.8 will be provided for the overall AE summary and subject incidence of TEAEs by MedDRA system organ class and preferred term for the Double-Blind Treatment Period, Open-Label Extension Period, and study overall.

At each level of summarization (e.g., any AE, system organ class, and preferred term), subjects experiencing more than one TEAE will be counted only once. In the summary of TEAEs by severity grade, subjects will be counted once at the highest severity reported at each level of summarization; in the summary of TEAEs by relationship, subjects will be counted once at the closest relationship to study drug. Related events include those reported as "Related" to study drug; events considered not related are those reported as "Not Related" to study drug.

Adverse event data will be presented in data listings by subject, treatment group, and event. Serious AEs and AEs leading to discontinuation of the study drug will be presented in separate data listings.

# 4.5.4 Deaths, Other Serious Adverse Events, and Adverse Events of Special Interest

All deaths during the study will be listed by subject, to include the primary cause of death. Serious AEs and AEs of Special Interest, including those that led to withdrawal, or interruption of the study drug, will be provided in separate subject data listings.

## 4.5.5 Clinical Laboratory Evaluation

All descriptive summaries of laboratory results will be based on data analyzed by the central laboratory and presented in conventional units. All data will be included in by-subject data listings. Laboratory measurements identified as abnormal (i.e., outside the normal range) will also be listed separately by subject, laboratory test, and unit. In addition, normal ranges provided by the central laboratory will be presented in a separate listing.

Clinical laboratory measurements, including serum chemistry, hematology, coagulation, and thyroid function tests, will be summarized by treatment group and all subjects combined for each study treatment period. Descriptive statistics will be presented for observed values and changes from baseline at each visit where parameters

were scheduled to be collected per the clinical study protocol. A summary by safety subgroups of interest (type of cholestatic disease and baseline eGFR) described in Section 4.4.7.8 will be provided for the univariate summaries of chemistry and hematology using the Safety Analysis Set and Open-Label Extension Analysis Set. Change from the initiation of OLE will also be presented in the Open-Label Extension Period summaries.

Where applicable, laboratory results will be classified as "low," "normal," or "high" with respect to the parameter-specific reference ranges (i.e., below the lower limit of the normal range, within the normal range, or above the upper limit of the normal range). Three-by-three contingency tables will be presented for each laboratory parameter to summarize the shift from the baseline category to the worst post-baseline measurement within each treatment period, defined as the value numerically farthest outside of the normal range across all post-baseline visits through the end of each study treatment period and the study overall. Shift from the initiation of OLE value to the worst post-OLE value will also be provided for the Open-Label Extension Period. Summary results will include the count and percentage of subjects within each shift category and treatment group separately for each study treatment period and the study overall.

Where applicable, hematology, chemistry and coagulation results for select parameters will be assigned a toxicity grade based on the U.S. Department of Health and Human Services CTCAE, version 5.0 (HHS 2017). If criteria for a grade includes a quantitative component and a clinical intervention component, the clinical intervention component will be ignored where it cannot be programmatically addressed using available data and only the quantitative portion of the criteria will be considered. If the quantitative criteria for grading are equivalent for two grades and the differentiation is described by clinical interventions, the clinical intervention component will not be considered and the highest CTCAE grade will be assigned. Similarly, death related to AE (i.e., Grade 5) cannot be determined with available laboratory-based data collection and, thus, will not be summarized as a category. Laboratory parameters that include multiple sets of criteria for each direction (e.g., separate criteria for potassium measures to assess hyperkalemia and hypokalemia) will be summarized separately to reflect each set of criteria.

Five-by-five contingency tables will be presented for lab tests where toxicity grading can be applied, to summarize the shift from the baseline grade to the worst post-baseline grade within each study treatment period and the study overall. Grades will be presented as none (Grade 0; i.e., measurements did not meet any CTCAE criteria for Grades 1 through 4), mild (Grade 1), moderate (Grade 2), severe (Grade 3), or life-threatening (Grade 4). Shift from the initiation of OLE value to the worst post-OLE value will also be provided for the Open-Label Extension Period. Summary results will include the count and percentage of subjects within each shift category, analyzed separately for each study treatment period.

The clinical study protocol includes algorithms for monitoring and interrupting study drug for treatment-emergent hepatocellular and cholestatic DILI signals based on ALT, ALP and total bilirubin values. A shift from baseline in ALT or ALP values to select treatment-emergent DILI signal criteria will be summarized for each study period and the study overall.

Subjects with post-baseline ALT values will be assessed for shift from Baseline ALT to the following DILI criteria:

Normal Baseline ALT:

- Any Instance of ALT  $\geq$  3 x ULN and Total Bilirubin  $\geq$  2 x Baseline
- Any Instance of ALT  $\geq$  5 x ULN
- Any Instance of ALT  $\geq$  8 x ULN

Elevated Baseline ALT (ALT > ULN at Baseline):

- Any Instance of ALT  $\geq 2$  x Baseline and Total Bilirubin  $\geq 2 \times$  Baseline
- Any Instance of ALT  $\geq$  3 x Baseline
- Any Instance of ALT  $\geq$  5 x Baseline

Subjects with post-baseline ALP values will be assessed for shift from Baseline ALP to the following DILI criteria:

- Any Instance of ALP  $\geq 2$  x Baseline and Total Bilirubin  $\geq 2$  x Baseline
- Any Instance of ALP  $\geq$  3 x Baseline

Summary results will include the count and percentage of subjects within each shift category, analyzed separately for each study treatment period and the study overall.

Subjects qualifying in any of the above ALT or ALP treatment-emergent DILI criteria will be presented in a data listing to include ALT (or ALP), baseline and treatment-emergent total bilirubin, baseline and treatment-emergent direct bilirubin, Gilbert Syndrome status, and any treatment-emergent AEs reported at the time of the treatment-emergent lab date.

The clinical study protocol also includes algorithms for monitoring and interrupting study drug for treatment-emergent acute deterioration of kidney function based on laboratory parameters or clinical symptoms. Any increase in serum creatinine by  $\geq 0.3$  mg/dL from baseline and any increase in serum creatinine to  $\geq 1.5$  x baseline will be summarized for each study period and the study overall.

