## 9.4. Study Visits

Subjects should fast for at least 8 hours before each dose of study drug and before study visits that require a blood sample for assessment of chemistry, PK (predose), or completion of questionnaires. The date, time, and type of any snack or meal provided at the site will be recorded. Water is acceptable in the morning of study visits to ensure the subject is hydrated for laboratory sample collection.

Questionnaires to be completed at the site should be administered in a quiet, private place at the study site before all other scheduled procedures.

For the hybrid model, Visits 1, 2, 6, and 8 (Screening, Day 1, Week 6, and Week 12) and early termination (if applicable) must be completed at the study site. All other study visits may be conducted remotely, where allowed per regulatory/local requirements. For the decentralized model, all visits will be conducted remotely.

For remote visits for both the hybrid and decentralized models, the home health nurse visit at the subject's home or work and the telemedicine visit with the study site staff for a given study visit may be conducted on different days but must be within the allowable visit window. The home health nurse will complete the study assessments that the site is physically unable to complete remotely (eg, blood and lab sample collection, vital signs, ECGs); the site will complete all other study assessments remotely during the telemedicine visit. Additional information for conducting remote visits will be provided in study-specific manual(s).

Study procedures are listed for each visit in the following sections and summarized in the Schedule of Assessments ([Appendix A](#)). Further details regarding efficacy and PD, safety, and PK assessments are located in [Sections 11, 12, and 13](#), respectively.

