### **Abnormal Laboratory Values or Vital Signs**

Protocol defined laboratory values and vital signs will be reported as AEs if the abnormal laboratory or vital sign result:

- Requires an adjustment in the study drug(s) or discontinuation of treatment;
- Requires additional testing, excluding repeat testing of the lab in question, or surgical intervention;
- Is associated with accompanying signs/symptoms that are not considered part of a pre-existing diagnosis or syndrome; or
- Is considered clinically significant by the Investigator.

If an abnormal laboratory value or vital sign is the result of an evaluation of clinical signs, symptoms, or suspected diagnosis during the conduct of the study, the signs/symptoms or diagnosis should be reported as an AE (or if appropriate, an SAE) only if clinically significant, and the associated laboratory value or vital sign should be considered additional information that must be collected on the relevant eCRF.

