**Table 7: Algorithm for Monitoring and Interrupting Study Drug for Treatment-Emergent Cholestatic DILI Signals**

Treatment-Emergent ALP	Bilirubin	Liver-Related Symptoms	Action
ALP $\geq 2\times$ baseline without alternative explanation	Normal Gilbert's syndrome or hemolysis: No change in baseline total bilirubin	None	Repeat blood tests and monitor for symptoms.
	Total bilirubin $\geq 2\times$ baseline Gilbert's syndrome or hemolysis: direct bilirubin $> 2\times$ baseline if baseline $> 0.5$ mg/dL	None or present	Interrupt study drug and repeat blood tests. Study drug can be restarted if another etiology (not cholestatic injury) is identified and abnormalities return to baseline levels.
	Normal or elevated	Present	
ALP $\geq 3\times$ baseline without alternative explanation	Normal or elevated	None or present	

ALP = alkaline phosphatase; DILI = drug induced liver injury.

In addition to the algorithms above, the Investigator may use clinical judgement to increase monitoring for DILI or interrupt or discontinue study drug as warranted for reasons of subject safety. An episode of DILI leading to hepatic decompensation in a study subject will result in permanent study drug discontinuation.

If a subject cannot return to the study site for a scheduled or unscheduled visit, or an immediate assessment is required, the use of a local laboratory is acceptable at the discretion of the Investigator. All local laboratory values obtained as part of DILI monitoring as well as their normal ranges are to be collected and entered into the clinical database.

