### 14. STATISTICS

Summaries will be presented for both the Double-Blind Treatment Period and the Open-Label Extension Period separately. Data summaries will use descriptive statistics (n, mean, standard deviation, median, minimum, and maximum) for continuous variables and frequency and percentage for categorical and ordinal variables. Unless otherwise specified, endpoints will use the last pre-treatment value available prior to the first dose of study drug as baseline. All data collected will be included in subject data listings.

A formal Statistical Analysis Plan (SAP) will be prepared and finalized before database lock. Additional statistical analysis details will be included in the SAP.

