# 4.1.1 Reporting Conventions

In general, tables will be summarized by treatment group and overall. Summaries will be presented for both the Double-Blind Treatment Period and the Open-Label Extension Period separately. Tables summarizing data from the Open-Label Extension Period will summarize subjects by randomized treatment from the Double-Blind Treatment Period as well as by all subjects combined. In general, all data collected and any derived data will be presented in subject data listings, for all enrolled subjects. Listings will be ordered by site, subject number, treatment group, and assessment or event date. The treatment group presented in listings will be based on the planned assignment, unless otherwise noted.

In general, continuous variables will be summarized to indicate the study population sample size (N), number of subjects with available data (n), mean, SD, median, first (Q1) and third (Q3) quartiles, minimum, and maximum values. Categorical variables will be summarized by the population size (N), number of subjects with available data (n), number of subjects in each category, and the percentage of subjects in each category. Unless otherwise noted, the denominator to determine the percentage of subjects in each category will be based on the number of subjects with available data. Select ordinal data may be summarized using both descriptive statistics and counts and percentages of subjects in each category, as appropriate.

Non-zero percentages will be rounded to one decimal place. Rounding conventions for presentation of summary statistics will be based on the precision of the variable of summarization, as it is collected in its rawest form (i.e., on the eCRF or as provided within an external file) and are outlined as follows:

- The mean and median will be rounded to one more decimal place than the precision of the variable of summarization;
- Measures of variability (e.g., SD, SE) will be rounded to two more decimal places than the precision of the variable of summarization; and
- Minimum and maximum values will be presented using the same precision as the variable of summarization.

Other statistics (e.g., CIs) will be presented using the same general rules outlined above, or assessed for the most appropriate presentation based on the underlying data.

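### SAP 4.5.5 limits laboratory summaries to central data and makes no exception for the DILI-criteria table, so local liver values collected for DILI monitoring would not count in it

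*SAP*

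**What the plan says.** SAP 4.5.5 opens with a source rule: "All descriptive summaries of laboratory results will be based on data analyzed by the central laboratory and presented in conventional units". By-visit statistics, worst-value shifts, CTCAE-grade shifts and the DILI-criteria table then follow in that section. The DILI table counts subjects with any instance of eight criteria built from ALT, ALP and total bilirubin. A dedicated listing covers the subjects who qualify and adds bilirubin, Gilbert status and concurrent AEs. None of these displays restates or relaxes the source rule, and the only normal ranges mentioned are the central laboratory's.

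Protocol 12.13.3 foresees another source. It leaves use of a local laboratory to the Investigator's discretion in these circumstances: "If a subject cannot return to the study site for a scheduled or unscheduled visit, or an immediate assessment is required". It then requires capture in the study database: "All local laboratory values obtained as part of DILI monitoring as well as their normal ranges are to be collected and entered into" it.

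Two SAP rules come close to the point without settling it. Section 4.1.3 brings unscheduled-visit data into derivations such as the worst post-baseline value, but it concerns visit type, not laboratory. Section 4.1.1 says that, in general, "all data collected and any derived data will be presented in subject data listings", which secures display but not counting.

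**The concern.** The DILI table is the planned by-arm count of the protocol's own liver-monitoring criteria, and safety is a secondary objective. The protocol lets a local result serve that monitoring and has it captured with its range. The SAP's source rule, applied as written, then removes that result from the one table designed to count it.

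An any-instance count depends on single values. An urgent or off-site sample may be the only one that crosses a threshold, or the highest. At stake are the criterion-level count and tier by arm, and a place in the listing that joins liver tests, Gilbert status and AEs. The data themselves are not lost, and efficacy is not involved.

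**Working it through.** The plan states no figure on this point, so the check compares the texts and adds arithmetic for scale.

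**1. When a local value changes the table (literal reading)**

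- A central value meets a criterion and the local repeat is no higher: no change.
- A central value meets a lower tier and the local repeat meets a higher one (for example ALT ≥5× ULN centrally, then ≥8× ULN locally): the subject is counted, but in the lower tier only.
- The first or only qualifying value is local: the subject is missing from the table and from the DILI listing.
- The central trigger is a protocol row with no SAP counterpart and the local repeat reaches an SAP criterion (for example ALP ≥2× baseline centrally, then ≥3× locally): also missing from both.

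**2. How protocol rows map to SAP criteria**

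Protocol Tables 5, 6 and 7 have 4 + 4 + 4 = 12 rows, setting aside the Gilbert/hemolysis variants. The SAP lists 3 + 3 + 2 = 8 criteria. Nine rows map to those eight, because both ALT ≥5× ULN rows of Table 5 map to one criterion. Three rows have no counterpart: ALT ≥2× baseline with symptoms, ALP ≥2× baseline alone, and ALP ≥2× baseline with symptoms. Most central triggers are therefore already counted at their own tier, and full omission is confined to the last two cases in step 1.

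**3. How far AE reporting covers the loss**

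Protocol 12.1.4.1 makes a laboratory abnormality an AE if, among other conditions, it "Requires an adjustment in the study drug(s) or discontinuation of treatment". If interruption counts as an adjustment, six of the eight SAP criteria correspond to interruption rows and should also surface as AEs (for ALP, when there is no alternative explanation). The other two are ALT ≥5× ULN with a normal baseline and ALT ≥3× baseline with an elevated baseline. Without symptoms and with normal bilirubin, the protocol's action for these is to repeat the tests and monitor, and 12.1.4.1 excludes repeat testing of the same laboratory test as a trigger. Such a value becomes an AE only if another condition applies, such as clinical significance in the Investigator's judgement. The AE route is partial.

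**4. Scale**

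The documents give no frequency of local testing. For one subject qualifying only on a local value:

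- 1/29 = 3.4% of an arm (exact 95% CI 0.1 to 17.8%), against 0/29 = 0% (0 to 11.9%) if the value is excluded
- 1/58 = 1.7% of all subjects

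**5. Why the ULN must be named**

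Assume a local ALT of 220 U/L in a subject with normal baseline ALT, a central ULN of 40, and a local ULN of 35 or 55 (illustrative values, not from the documents):

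- 220/40 = 5.5
- 220/35 = 6.3
- 220/55 = 4.0

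The ≥5× ULN result depends on the ULN chosen, and the SAP does not say which applies to a local value.

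**The case against.** The strongest objection is that the SAP may already be adequate on either reading. Read broadly, it prespecifies a central-only rule, which gives one assay and one set of ranges. Read narrowly, the rule covers by-visit descriptive statistics only: Protocol 14 pairs descriptive statistics with continuous variables and uses counts and percentages for categorical ones. The count tables would then be unrestricted, and SAP 4.1.3 would admit unscheduled values.

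Part of this stands. Central-only is defensible for by-visit statistics and for the general worst-value and CTCAE shifts, so a reader who infers that those tables must also take local values goes further than the documents support. The DILI table differs because it tallies criteria for which the protocol itself accepts local results. The narrow reading is possible, but the opening rule says all, the later tables are also described as summaries, and no ULN is given for local values. Two programmers could produce different tables.

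Three stronger inferences fail:

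- **Local testing is common.** Planned chemistry on Days 22, 43, 64 and 85 leaves 63 of 84 days (75%) in three 21-day intervals. A gap between planned tests does not show that an unscheduled sample would go to a local laboratory. At remote visits, "The home health nurse will complete the study assessments that the site is physically unable to complete remotely (eg, blood and lab sample collection" among them, which lowers the need.
- **Central-only counts are biased low.** They can only be lower than a count that pools both sources, which does not make them wrong. Pooling can add crossings due to range differences. With an assumed central baseline ALT of 80 and a local value of 250, the plain ratio is 250/80 = 3.13 and meets ≥3×. Scaled by assumed ULNs of 40 (central) and 55 (local), it is (250/55)/(80/40) = 2.27.
- **The event disappears.** Local values reach the by-subject listings, SAP 4.5.5 adds a separate listing of abnormal values, and the DMC reviews AEs of Grade 3 or higher.

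The Data Management Plan and table templates are not available here and might address local values. A rule on which values count in a by-arm safety table still belongs in the SAP, whose stated purpose is to avoid post hoc decisions.

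**Conclusion.** The point holds as a minor one, limited to the DILI-criteria table and its listing. The stated source rule gives a less complete count than the collected data allow, and AE reporting only partly makes up for it. This assumes that the rule is applied literally and that at least one subject has a local value that is the only or highest qualifying one. The number of such subjects is unknown and may be zero. Each would move an arm's count, or its tier, by 3.4 percentage points. No efficacy result and no collected data point is affected.

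**What to change.** In SAP 4.5.5, keep by-visit statistics and the general worst-value and CTCAE shift tables central-only. Add that local ALT, ALP and bilirubin values collected for DILI monitoring count toward the DILI-criteria table and its listing, flagged by source. State that ULN-based criteria are judged against the ULN of the laboratory that reported the value, and that baseline-multiple criteria are applied as the protocol states them.

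The cost is a few sentences and modest programming, since the values and ranges are already collected. The downside is that some between-laboratory assay and range differences enter this one table; the source flag makes them visible. The change should be made before unblinding.
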